#### **9.8. Quality Control**

All data abstracted from the Definitive Oncology Dataset by CRNs will undergo an independent quality control review, with evaluation for consistency, completeness, and outlier values. This review is conducted by a supervising Project Curation Manager at Concerto HealthAI and through programmatic evaluation of study data. Data queries generated as part of quality review are documented and resolved, with documentation of queries and resolution maintained in a complete query log.

Data housed in electronic case report forms will then be exported to SAS datasets for data cleaning and preparation, creation of derived values, and preparation of analysis datasets. Data will then undergo initial statistical review, including examination of all fields for outlier values, and evaluation for internal consistency of study data. Values that are flagged as potentially anomalous during statistical review will be queried and resolved before analysis datasets are finalized. All study data also undergo scientific review of study results prior to data lock.

### **9.9. Limitations of the Research Methods**

1. This study reflects treatment practice patterns only within the United States who are part of the Definitive Oncology Dataset. The majority of the data reflects treatment in community oncology settings (80%). It is possible that treatment patterns may differ in academic centers compared with community settings.
2. This study is retrospective. With the advent of newer therapies in AML, it is expected that treatment patterns will change during the next few years, and therefore, this study may not be reflective of future AML treatment patterns.
3. This study reflects a convenience sample of patients. It is possible that patients within the Definitive Oncology Dataset differ from the underlying AML population in ways that may not be measurable. For this study, all patients in the Definitive Oncology Dataset with evidence of Mylotarg utilization and an AML diagnosis will be selected, however.
4. Some measurements may not be consistently available from patient records in the Definitive Oncology Dataset.

### **9.10. Other Aspects**

Not applicable.

## **10. PROTECTION OF HUMAN SUBJECTS**

### **10.1. Patient Information**

Concerto HealthAI and Pfizer may provide the other party with access to certain information that can be used by itself or in combination with other available information to identify a specific individual included in the study (“patient personal data”) so long as prior written approval of the party receiving the materials is obtained. For sake of clarity, key-coded data relating to individual persons is considered to be personal data. Neither Concerto HealthAI nor Pfizer will attempt to re-identify study subjects. Both parties will implement appropriate internal measures to minimize the risk of any re-identification of study subjects.

All parties will comply with all applicable laws, including laws regarding the implementation of organizational and technical measures to ensure protection of patient personal data, and in accordance with the Pfizer/Concerto HealthAI Collaboration Agreement. Such measures will include omitting patient names or other directly identifiable data in any reports,

publications, or other disclosures, except where required by applicable laws or where there is valid written consent or authorization on file.

The party sharing patient personal data or samples is responsible for providing and obtaining any legally-required notice and consent from individuals, or for arranging for the study investigator and site to obtain such notice and consent from individuals, with respect to such patient personal data or samples for the purposes contemplated by this Protocol.

In case of data transfer, processing and use, both Concerto HealthAI and Pfizer will maintain high standards of confidentiality and protection of patients' personal data consistent with applicable privacy laws.

Neither Concerto HealthAI nor Pfizer will transfer, or permit any third party to transfer personal data provided by the other party across any national borders without prior written consent of the party providing such data, unless specifically authorized to do so. In the event any such cross-border transfer is authorized, the party transferring such personal data across national borders is responsible for ensuring that any transfer of personal data across national borders (whether performed by itself or a third party) complies with all applicable laws.

Concerto HealthAI and Pfizer will ensure that any patient personal data it is authorized to process is not processed in a way that is incompatible with the purposes for which it was collected or subsequently authorized by the individual from whom it was obtained. For the sake of clarity, the process of de-identification does not render the data incompatible for the purposes for which it was collected for this study.

Concerto HealthAI and Pfizer will apply adequate and commercially reasonable electronic, physical, and other safeguards appropriate to the nature of the information to prevent any accidental, unauthorized or unlawful use, access, alteration, loss or disclosure of personal data.

## **10.2. Patient Consent**

As this study does not involve data subject to privacy laws according to applicable legal requirements, obtaining informed consent from patients by Pfizer is not required.

## **10.3. Institutional Review Board (IRB)/Independent Ethics Committee (IEC)**

There must be prospective approval of the study protocol, protocol amendments, and other relevant documents (eg, informed consent forms if applicable) from the relevant IRBs/IECs. All correspondence with the IRB/IEC must be retained. Copies of IRB/IEC approvals must be forwarded to Pfizer.

## **10.4. Ethical Conduct of the Study**

This study will be conducted in accordance with legal and regulatory requirements, as well as with scientific purpose, value and rigor and follow generally accepted research practices described in Good Practices for Outcomes Research issued by the International Society for Pharmacoeconomics and Outcomes Research (ISPOR).

## 11. MANAGEMENT AND REPORTING OF ADVERSE EVENTS/ADVERSE REACTIONS

### 11.1. Structured Data Analysis

This study involves data that exist as structured data by the time of study start.

In these data sources, individual patient data are not retrieved or validated, and it is not possible to link (ie, identify a potential association between) a particular product and medical event for any individual. Thus, the minimum criteria for reporting an adverse event (AE) (ie, identifiable patient, identifiable reporter, a suspect product, and event) cannot be met.

### 11.2. Human Review of Unstructured Data

This study protocol requires human review of patient-level unstructured data; unstructured data refer to verbatim medical data, including text-based descriptions and visual depictions of medical information, such as medical records, images of physician notes, neurological scans, X-rays, or narrative fields in a database. The reviewer is obligated to report AEs with explicit attribution to any Pfizer drug that appear in the reviewed information (defined per the patient population and study period specified in the protocol). Explicit attribution is not inferred by a temporal relationship between drug administration and an AE, but must be based on a definite statement of causality by a healthcare provider linking drug administration to the AE.

The requirements for reporting safety events on the non-interventional study (NIS) adverse event monitoring (AEM) Report Form to Pfizer Safety are as follows:

- All serious and non-serious AEs with explicit attribution to **any Pfizer drug** that appear in the reviewed information must be recorded on the NIS AEM Report Form and reported, within 24 hours of awareness, to Pfizer Safety using the NIS AEM Report Form.
- Scenarios involving drug exposure, including exposure during pregnancy, exposure during breast feeding, medication error, overdose, misuse, extravasation, lack of efficacy, and occupational exposure associated with the use of a Pfizer product must be reported, within 24 hours of awareness, to Pfizer Safety using the NIS AEM Report Form.

For these AEs with an explicit attribution or scenarios involving exposure to a Pfizer product, the safety information identified in the unstructured data reviewed is captured in the Event Narrative section of the report form, and constitutes all clinical information known regarding these AEs. No follow-up on related AEs will be conducted.

All the demographic fields on the NIS AEM Report Form may not necessarily be completed, as the form designates, since not all elements will be available due to privacy concerns with the use of secondary data sources. While not all demographic fields will be completed, at the very least, at least one patient identifier (eg, gender, age as captured in the narrative field of the form) will be reported on the NIS AEM Report Form, thus allowing the report to be considered a valid one in accordance with pharmacovigilance legislation. All identifiers will be limited to generalities, such as the statement “A 35-year-old female...” or “An elderly male...” Other identifiers will have been removed.

Additionally, the onset/start dates and stop dates for “Illness”, “Study Drug”, and “Drug Name” may be documented in month/year (MMM/YYYY) format rather than identifying the actual date of occurrence within the month /year of occurrence in the day/month/year (DD/MMM/YYYY) format.

All research staff members must complete the following Pfizer training requirements:

- “YRR Training for Vendors Working on Pfizer Studies (excluding interventional clinical studies and non-interventional primary data collection studies with sites/investigators)”.

These trainings must be completed by research staff members prior to the start of data collection. All trainings include a “Confirmation of Training Certificate” (for signature by the trainee) as a record of completion of the training, which must be kept in a retrievable format. Copies of all signed training certificates must be provided to Pfizer.

## **12. PLANS FOR DISSEMINATING AND COMMUNICATING STUDY RESULTS**

The final study report will be completed by Concerto HealthAI and is estimated to be available in July 2020.

In the event of any prohibition or restriction imposed (eg, clinical hold) by an applicable competent authority in any area of the world, or if Concerto HealthAI is aware of any new information which might influence the evaluation of the benefits and risks of a Pfizer product, Pfizer should be informed immediately.

### **14. LIST OF TABLES**

None.

### **15. LIST OF FIGURES**

None.

### **16. ANNEX 1. LIST OF STAND ALONE DOCUMENTS**

None.

### **17. ANNEX 2. ENCEPP CHECKLIST FOR STUDY PROTOCOLS**

Not Applicable.

### **18. ANNEX 3. ADDITIONAL INFORMATION**

Not Applicable.

## REVISION HISTORY

SAP Version 1.0 (April 1, 2020)

SAP Version 2.0 (September 9, 2020)

## 1. BACKGROUND AND RATIONALE

Acute myeloid leukemia (AML) is characterized by proliferation of leukemic blasts in the bone marrow and other tissues and, if untreated, is a rapidly fatal disease. In the United States (US) in 2019, it was estimated there would be 21,450 new cases and 10,920 deaths from AML. The average age at diagnosis is 68 years old, and the 5-year survival rate is 26.9%. About 60%-70% of adults with AML can attain a complete remission following induction therapy with cytotoxic chemotherapies to reduce leukemic cells in the blood and bone marrow. Slightly more than 25% (45% of those who attain complete remission) are expected to survive 3 or more years and may be cured. Remission rates are related to age, with the expected remission rate of more than 65% in those younger than 60 years old. Duration of remission is shorter in older patients, and increased morbidity and mortality during induction treatment are related to older age.

Historically, the number of treatments available for newly diagnosed patients with AML has been limited. However, new treatment regimens have become available recent years (including gemtuzumab ozogamicin [GO], midostaurin, glasdegib, plus low-dose cytarabine, venetoclax plus hypomethylating agents). Given the FDA label for GO, issued September 2017, it is critical to understand the recent real-world use of GO as a treatment for AML.

Additional information regarding the background and rationale for the study is contained in the study protocol.

## 2. OBJECTIVES

The study includes patients with a diagnosis of AML who received Mylotarg (Gemtuzumab ozogamicin) in a real-world setting.

The study objectives are as follows. All analyses as described in Objectives 1 through 4 will be assessed across all patients using Mylotarg and will not be stratified by a grouping variable.

1. To describe the demographic and clinical characteristics as outlined in the variable list below for patients diagnosed with AML who received Mylotarg in a real-world setting.
  - a. Demographic characteristics will include age, race, body mass index (BMI), insurance status, and region of residence closest to the date of AML diagnosis.
  - b. Clinical characteristics will include comorbidity scores, Eastern Cooperative Oncology Group (ECOG) score, and disease characteristics such as stage at index date, cytogenetic testing results at index date, and de novo versus secondary AML diagnosis.
2. To describe the treatment patterns from the diagnosis of AML through the end of the third relapsed/refractory (R/R)-based line of therapy (R/R event, or disease progression, or death are considered as end events).

- a. Distribution of regimens within lines, for the first 3 R/R-based lines of systemic therapy.
  - b. Distribution of regimen sequences, across the first 3 R/R-based lines of systemic therapy.
  - c. Starting dose and dose changes of Mylotarg in each of the first 3 R/R-based lines of therapy.
  - d. Duration of Mylotarg treatment in each of the first 3 R/R-based line of therapy.
3. To describe the effectiveness outcomes of treatment of AML patients who received Mylotarg in a real-world setting.
    - a. Real-world event-free survival (rwEFS)/real-world relapse-free survival (rwRFS) in the first 3 R/R-based lines of therapy. The definition of rwEFS/rwRFS as described in [Section 4.3.2](#) is aligned to the extent possible using real-world data with that used by Pfizer in other studies.
    - b. Real-world overall survival (rwOS) from start of the initial line of therapy in which Mylotarg is used.
    - c. rwEFS/rwRFS/rwOS will be described across all patients.
  4. To evaluate response for each regimen in the first qualifying Mylotarg-containing R/R-based line of therapy among AML patients who received Mylotarg in a real-world setting.
    - a. First and best response, as outlined in [Section 4.3.6](#) will be described for each regimen in the first qualifying Mylotarg-containing R/R-based line of therapy.
    - b. Time to best response will be described for each regimen in the first qualifying Mylotarg-containing R/R-based line of therapy.
    - c. Duration of best response will be described for each regimen in the first qualifying Mylotarg-containing R/R-based line of therapy.

### 3. RESEARCH METHODOLOGY

#### 3.1. Study Design

This is a retrospective, observational study of characteristics, treatment patterns, and clinical outcomes in patients diagnosed with AML who received Mylotarg. The study will use oncology electronic medical record (EMR) data available to Concerto HealthAI, including data from CancerLinQ-affiliated practices. These data are referred to as the Definitive Oncology Dataset. All study data are secondary data and will have been collected retrospectively from existing clinical data originally collected as part of routine care.

### 3.2. Study Setting

The Definitive Oncology Dataset is used in support of a range of business activities, including retrospective research and is not aggregated specifically to address the research of any one study.

The Definitive Oncology Dataset is drawn from a wide range of principally community oncology practices throughout the United States. Practices range in size from very small to large, and are located in both rural and urban settings. The practices are not all members of any one group purchasing organization, so practice patterns reflect real-world variability of treatment.

Datasets available to Concerto HealthAI include a repository of oncology healthcare data, including those from practices affiliated with CancerLinQ — a wholly-owned subsidiary of the American Society of Clinical Oncology that works with both nonprofit and federal agencies to warehouse and aggregate medical records of cancer patients treated at practices in 40 US states and the District of Columbia — as well as administrative healthcare claims and genomic data.

### 3.3. Study Size

CCI

Initial exploration of the Definitive Oncology Dataset suggests the study sample size will be between 20 and 30 patients. The aims of this research are descriptive. Accordingly, statistical power for inferential testing comparing effectiveness outcomes across groups is not indicated. Therefore, power calculation is not applicable.

### 3.4. Eligibility Criteria

#### 3.4.1. Inclusion Criteria

Patients must meet all of the following inclusion criteria to be eligible for inclusion in the study:

1. Confirmed diagnosis of AML on or after 01 December 2014 through Clinical Research Nurse (CRN) review of provider documentation of AML diagnosis in the medical record.
2. Receipt of Mylotarg at any point during first 3 R/R-based lines of therapy following initial AML diagnosis date occurring on or after 9/1/2017.
3. Age  $\geq 18$  years at initial diagnosis of AML.

There are no inclusion criteria related to minimum follow-up.

### 3.4.2. Exclusion Criteria

1. Record of 1 or more of the following confounding diagnoses at any point before or after AML diagnosis: Acute lymphoblastic leukemia; acute promyelocytic leukemia, aggressive systemic mastocytosis; hypereosinophilic syndrome and/or chronic eosinophilic leukemia; dermatofibrosarcoma protuberans; gastrointestinal stromal tumors.

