## 3.5. Study Measures

### 3.5.1. Data Elements

#### 3.5.1.1. Curated Data

Data abstracted for eligible patients from the unstructured data available in the Definitive Oncology Dataset by CRNs will include the following:

- Race/Ethnicity ([Table 1](#)).
- Date of initial AML diagnosis. This date defines the *index date* for the study, as referenced below in describing other study variables ([Table 1](#)).
- Documentation of de novo versus secondary AML at index date. Secondary AML is defined as development of AML after myelodysplastic syndromes (MDS), myeloproliferative neoplasms (MPN), or following exposure to chemotherapy and/or radiotherapy ([Table 2](#)):
  - If secondary AML, documentation of use of hypomethylating agents (HMA) at any point prior to initial AML diagnosis (Y/N). If yes, name of HMA agent will be documented.
- Stage at index date ([Table 2](#)).
- Comorbidities, indicated as present versus not indicated as present at index date ( $\pm 30$  days). The conditions to be assessed will include those assessed as part of the standard Charlson Comorbidity Index. These include myocardial infarction, congestive heart failure, peripheral vascular disease, cerebrovascular accident, hemiplegia, chronic obstructive pulmonary disease, ulcer disease, diabetes, renal disease, connective tissue disease such as rheumatoid arthritis or lupus, Alzheimer's or other dementia, cirrhosis or other serious liver disease, leukemia (other than AML), lymphoma, metastatic solid tumor, and Human Immunodeficiency Virus (HIV)/acquired immunodeficiency syndrome (AIDS). The Charlson Comorbidity Index will be computed ([Table 2](#)).
- ECOG performance status, if available, or indication of impaired performance status not otherwise classified as an ECOG rating, at index date ( $\pm 30$  days) ([Table 2](#)).

- First response and best overall response to treatment from the index date through the end of the first R/R-based line of therapy or the end of the record, whichever occurs first (Table 9-Table 11, Table 14-Table 15).
- Biomarker status and date of results will be recorded at index date ( $\pm 30$  days) (Table 2).

Biomarkers collected will include:

- IDH1
- IDH2
- TP53
- Intermediate Risk
  - FLT3
  - NPM1.

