rwEFS will be defined as the time from the treatment initiation date (for the first line of Mylotarg-containing therapy) to the date of treatment failure (TF), relapse from CR or better, or death from any cause, whichever comes first. TF is defined as failure to achieve CR or better following up to 3 cycles of Mylotarg. Accordingly, the time origin for rwEFS will be the start of Mylotarg in the first line of therapy in which it is used. The terminal event for analysis of rwEFS is the earlier of treatment failure, relapse from CR or better (as evidenced by provider documentation), or death. Patients who have not died or experienced an event by the date of last contact within the medical record will be censored for analysis of rwEFS.

rwRFS will be defined as the time from the treatment initiation date (during the first line of Mylotarg-containing therapy) to the date of a relapse event, or death from any cause, whichever comes first. The time origin for rwRFS will be the start of Mylotarg in the first line of therapy in which it is used. The terminal event for analysis of rwRFS will be the earlier of a relapse event (as evidenced by provider documentation), or death. Patients who have not died or experienced a relapse event by the date of last contact within the medical record will be censored for analysis of rwRFS.

The time origin of rwOS analysis is the start of the first Mylotarg use. The terminal event for analysis of rwOS is date of death. Note that Social Security Disability Insurance (SSDI) records have an expected lag of up to 4 months. Accordingly, patients who are not indicated to be deceased in clinical records or SSDI records will be censored for rwOS analysis as of the later of 1) the latest date known alive within the clinical record, 2) 4 months prior to the date of most recent SSDI update.

Separate Kaplan-Meier analyses will be conducted for each rwEFS, rwRFS and rwOS endpoint.

#### 4.3.6. Methods under Objective 4

*Objective 4: To evaluate response among AML patients who received Mylotarg in a real-world setting.*

- a. First and best response for each regimen in the first qualifying Mylotarg-containing R/R-based line of therapy.
- b. Time to best response for each regimen in the first qualifying Mylotarg-containing R/R-based line of therapy.
- c. Duration of best response for each regimen in the first qualifying Mylotarg-containing R/R-based line of therapy.

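### Excluding patients for listed diagnoses recorded after AML diagnosis, even after Mylotarg has started, makes eligibility depend on follow-up and tends to bias rwOS downward

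*SAP*

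**What the plan says.** The single exclusion criterion is worded identically in SAP 3.4.2 and Protocol 9.2.2: "Record of 1 or more of the following confounding diagnoses at any point before or after AML diagnosis". The list covers two other acute leukemias (lymphoblastic and promyelocytic), mastocytosis and eosinophilic disorders, and two solid tumors (dermatofibrosarcoma protuberans and gastrointestinal stromal tumor). Apart from calling these diagnoses confounding, neither document gives a reason for the part that looks forward in time.

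The surrounding definitions fix the timing:

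- The index date is the "Date of initial AML diagnosis" (SAP 3.5.1.1), so a record after AML diagnosis is a post-index record.
- A patient qualifies through "Receipt of Mylotarg at any point during first 3 R/R-based lines of therapy following initial AML diagnosis date occurring on or after 9/1/2017" (SAP 3.4.1, item 2).
- "There are no inclusion criteria related to minimum follow-up" (SAP 3.4.1), so the length of record varies between patients.
- "The time origin of rwOS analysis is the start of the first Mylotarg use" (SAP 4.3.5, Methods under Objective 3). The same section starts rwEFS and rwRFS at Mylotarg.
- "Initial exploration of the Definitive Oncology Dataset suggests the study sample size will be between 20 and 30 patients" (SAP 3.3).

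SAP 4.1 names rwEFS/rwRFS, rwOS and response as the primary endpoints.

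**The concern.** Whether a treated patient belongs to the cohort is decided partly by what happens after the outcome clock has started. A patient who dies two months after first Mylotarg has two months in which a new excluding record could appear. A patient followed for two years has two years. If the second patient has a stromal tumor recorded in month 20, every analysis loses that patient, including the 20 months of observed survival.

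Such a rule selects on a quantity related to the outcome. Survival is then estimated in a group from which longer-observed patients have been removed preferentially, and a reader of the report could not see that this had happened. The limitations (Protocol 9.9, SAP 5) and the missing-data section (SAP 4.4) do not mention it. No sensitivity analysis addresses it, and the table shells in SAP 7 contain no attrition table showing when exclusions arose.

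**Working it through.** The plan states no figure to reproduce: 20 to 30 is a feasibility count and power is declared not applicable. The check covers mechanism, direction and plausible size.

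**1. Mechanism.** Let mu be the yearly rate at which a listed diagnosis is recorded, independent of survival. The chance of removal for a patient observed t months is 1 − exp(−mu·t/12). The documents do not give mu. With an assumed mu of 3% per year:

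- t = 2: 1 − exp(−0.005) = 0.5%
- t = 24: 1 − exp(−0.06) = 5.8%

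**2. Direction and size for a survival endpoint.** One million patients were simulated with exponential survival from Mylotarg, uniform censoring over 0 to 31.9 months and an independent diagnosis time. Anyone whose diagnosis fell within observed time was dropped, and Kaplan-Meier was run with and without the drop. Inputs:

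- Maximum follow-up: 1 September 2017 (SAP 3.4.1) to the end of April 2020 (Protocol 6, planned end of data collection), 972 days / 30.4375 = 31.9 months.
- Median survival, scenario A: 10 months (assumption).
- Median survival, scenario B: from the 26.9% 5-year survival in SAP 1, with constant hazard assumed. −ln(0.269)/5 = 0.263 per year, and 12 × ln 2 / 0.263 = 31.7 months.
- mu: 0.5% to 10% per year (assumption).

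| mu per year | Expected removals, N = 20 to 30, A | Same, B | KM median A (no removal: 10.00) | KM median B (no removal: 31.71) |
|---|---|---|---|---|
| 0.5% | 0.07 to 0.11 | 0.11 to 0.16 | 9.96 | 31.57 |
| 1% | 0.14 to 0.21 | 0.21 to 0.31 | 9.93 | 31.42 |
| 3% | 0.42 to 0.64 | 0.63 to 0.94 | 9.80 | 31.06 |
| 5% | 0.70 to 1.05 | 1.02 to 1.53 | 9.67 | 30.67 |
| 10% | 1.35 to 2.03 | 1.97 to 2.96 | 9.37 | 29.73 |

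The median falls in every row, by about 0.4% at the lowest rate and about 6% at the highest. At 3% per year the rule removes 0.7% of patients observed for under 6 months and 5.7% (A) or 5.9% (B) of those observed for over 18 months, roughly eight times as many. Mean observed time in removed and kept patients is 14.7 and 8.5 months (A), and 18.8 and 12.6 months (B).

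**3. Weight of one patient.** 1/30 = 3.3% and 1/20 = 5.0%. Suppose half the cohort is event-free at 12 months (assumption, no censoring).

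- Removing one event-free patient: 9/19 = 47.4% (N = 20) or 14/29 = 48.3% (N = 30).
- Removing one patient who has already had an event: 10/19 = 52.6% or 15/29 = 51.7%.

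The second case matters for rwEFS and rwRFS. A patient who relapsed early, lived on and later had a listed diagnosis recorded takes an early event out of those curves, while the same removal takes a long survivor out of rwOS.

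**4. Chance that it happens at all.** With an assumed per-patient probability p of a post-index excluding record, the chance of at least one removal is 1 − (1 − p)^N. For p from 1% to 5% this is 18.2% to 64.2% (N = 20) and 26.0% to 78.5% (N = 30).

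**The case against.** **A later record may correct the first diagnosis.** A later entry of acute promyelocytic or acute lymphoblastic leukemia can show that the patient did not have the disease under study. Removing that patient is a diagnostic check, and it need not depend on long survival. This stands, and the fix keeps it. It does not cover a new stromal tumor or dermatofibrosarcoma, and the present wording does not separate the two situations.

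**A second tumor could contaminate the data.** SAP 4.2 builds regimens from anti-cancer agents without restricting them to AML, and SAP 4.3.6 takes response from physician notes often informed by scans. Care for another tumor could be misread as an AML regimen or response. The documents do not give this reason, but it is plausible. It calls for an attribution rule; it does not require deleting the patient from rwOS.

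**The effect is small beside sampling error.** This is correct. With an exponential 10-month median, N = 25 and no censoring, a 95% order-statistic interval for the median (8th to 18th values) runs on average from about 5.4 to 17.6 months. A shift from 10.0 to 9.8 would be invisible inside it. But the shift is systematic, undisclosed and avoidable.

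A reader might also infer three stronger points that the documents do not support:

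- *That one unverified record excludes while AML must be confirmed.* AML is confirmed by "Clinical Research Nurse (CRN) review of provider documentation of AML diagnosis in the medical record", but Protocol 9.6 has the CRNs verify the other eligibility criteria in each chart as well.
- *That the rule contradicts Protocol 9.9, which says all Mylotarg-treated AML patients are selected.* That sentence qualifies a limitation about convenience sampling and is read subject to the eligibility criteria.
- *That the rule is inconsistent with keeping patients who have "leukemia (other than AML), lymphoma, metastatic solid tumor".* Those are Charlson items describing patients at baseline and say nothing about the exclusion.

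**Conclusion.** The point holds as a selection problem of probably small size. Both documents condition eligibility on information arising after index and after treatment start, and patients with longer survival or longer records are more exposed to removal. This tends to lower rwOS. The direction rests on diagnosis times independent of survival and on a survival-type endpoint.

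A reader might infer that rwEFS and rwRFS are biased downward as well, or that every removed patient is among the longest survivors. Neither follows. The simulation did not model relapse or treatment failure separately, a removed patient may already have had an event, and longer follow-up raises the chance of removal without deciding who is removed.

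The size cannot be derived from the documents. Over the assumed 0.5% to 10% per year, expected removals run from 0.07 to about 3 patients and the median falls by about 0.4% to 6%. The true number may be zero. The change is still worth making because one patient is 3.3% to 5.0% of the cohort and nothing planned would reveal the removal.

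**What to change.** In SAP 3.4.2 and Protocol 9.2.2:

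1. Limit the exclusion to listed diagnoses recorded on or before the date of first Mylotarg.
2. Let a later record exclude only where the CRN documents that it revises the original AML diagnosis, for example to acute promyelocytic or acute lymphoblastic leukemia.
3. Retain all other patients and list the later diagnosis. Do not count therapy or response documented as being for the second tumor as an AML regimen or response.

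The planned end of data collection was April 2020 and SAP version 2.0 is dated September 2020, so screening may already be complete. In that case, report the number and timing of post-index exclusions. If there are none, one sentence closes the matter. If there are any, repeat rwOS, rwEFS and rwRFS with those patients retained.

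The cost is a short edit to each document and a date condition in screening, plus chart abstraction for any patient already excluded, since study data are collected only for eligible patients (Protocol 9.6). The downside is that one or two patients with a later second malignancy may stay in the cohort.
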